8.2.1.2 Classification of Adverse Events

Severity of Adverse Events

The severity of all AEs will be assessed by the Investigator and graded as follows:

- **Mild:** requires minimal or no treatment and do not interfere with the subject's daily activities;
- **Moderate:** results in a low level of inconvenience or concern and may cause some interference with functioning;
- **Severe:** interrupts a subject's usual daily activity and may require systemic drug therapy or other treatment. Severe events are usually potentially life-threatening or incapacitating. The term "severe" does not necessarily equate to "serious".

Relationship of Adverse Events

All AEs must have their relationship to study intervention assessed by the Investigator who examines and evaluates the subject based on temporal relationship and his/her clinical judgment. The degree of certainty about causality will be graded using the categories below. In a clinical study, the IP must always be suspect.

- **Unrelated:** no reasonable possibility that the administration of the IP caused the event, no temporal relationship between the IP and event onset, or an alternate etiology has been established.
- **Related:** is known to occur with the IP, is a reasonable possibility that the IP caused the AE, or there is a temporal relationship between the IP and event. Reasonable possibility means that there is evidence to suggest a causal relationship between the IP and the AE.

Expectedness

An AE or suspected adverse reaction is considered “unexpected” if it is not listed in the Investigator’s Brochure (IB), package insert, or device labeling or is not listed at the specificity or severity that has been observed; or, if an IB is not required or available, is not consistent with the risk information described in the protocol, as amended. “Unexpected,” as used in this definition, also refers to AEs or suspected adverse reactions that are mentioned in the IB, package insert, or device labeling as occurring with a *class of drugs* (or other medical products) or as anticipated from the pharmacological properties or other characteristics of the IP, but are not specifically mentioned as occurring with the particular IP under investigation.

The Investigator will be responsible for determining whether an AE is unexpected, i.e., if the nature, severity, or frequency of the event is not consistent with the risk information previously described for the IP.

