8.2.1.1 Definitions

An AE is any untoward medical occurrence in a patient or clinical study subject, temporally associated with the use of study intervention, whether or not considered related to the study intervention. An AE can therefore be any unfavorable and unintended sign (including an abnormal laboratory finding), symptom, or disease (new or exacerbated) temporally associated with the use of study intervention.

An AE or suspected adverse reaction is considered "serious" if, in the view of either the Investigator or Sponsor, it results in any of the following outcomes:

- Death,
- A life-threatening AE,
- Inpatient hospitalization or prolongation of existing hospitalization,
- A persistent or significant incapacity or substantial disruption of the ability to conduct normal life functions, or
- A congenital anomaly or birth defect.

Important medical events that may not result in death, be life-threatening, or require hospitalization may be considered serious when, based upon appropriate medical judgment, they may jeopardize the subject and may require medical or surgical intervention to prevent one of the outcomes listed in this definition.

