8.2.1.3 Adverse Event Reporting Requirements

According to federal regulations, an Investigator must immediately (within 24 hours) report to the Sponsor or a designee any SAE, whether or not considered drug related, including those listed in the protocol or IB and must include an assessment of whether there is a reasonable possibility that the drug caused the event.

According to federal regulations, the Sponsor must notify the FDA and all participating Investigators as soon as possible, but in no case later than 15 calendar days after the Sponsor determines that a potential serious risk arising from a clinical study qualifies for reporting. Sponsor must report any suspected adverse reaction that is both serious and unexpected. The Sponsor must report an AE as a suspected adverse reaction only if there is evidence to suggest a causal relationship between the drug and the adverse event (See 21 CFR 312.32(c)(1)).

Furthermore, the Sponsor must also notify FDA of any unexpected fatal or life-threatening suspected adverse reaction as soon as possible but in no case later than 7 calendar days after the Sponsor's initial receipt of the information (See 21 CFR 312.32(c)(2)).

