9.7.1.6.1. Adverse Events

AEs are coded using MedDRA Version 24.1. Treatment-emergent adverse events (TEAE) are defined as events that start on or after the date of first dose of double-masked study drug up to and including the last dose of double-masked study medication. Ocular AEs are defined as those events for which an eye has been specified (OD, OS, or OU).

Ocular and non-ocular AEs will be summarized separately. Ocular AEs will be presented by study eye and non-study eye and overall (OU) if an event occurs in either eye.

In all summaries of AEs, percentages are calculated based on the number of subjects in each treatment group of the Safety Analysis Set.

Overall summaries of AEs by treatment will include:

- the number of AEs and SAEs reported;
- the number and percentage of subjects who experienced any AE;
- the number and percentage of subjects who experienced any serious adverse event (SAE) and the reason for seriousness;
- the number and percentage of subjects with any AE by worst severity and worst relationship.

The overall summaries of TEAEs will also include:

- the number and percentage of subjects with any TEAEs leading to discontinuation of double-masked study drug;
- the number and percentage of subjects with any TEAEs leading to study termination.

Summaries of the frequency and percentage of subjects with AEs by SOC and preferred term by treatment group will include:

- All AEs by SOC and preferred term;
- All AEs by SOC, preferred term, and maximum severity;
- All AEs by SOC, preferred term, and maximum relationship.

System organ class (SOC) will be sorted alphabetically, and preferred term (PT) within each SOC will be sorted by overall descending order of frequency according to the following rules in order:

1. Descending frequency within VVN539, 0.04%
2. Descending frequency within VVN539, 0.02%
3. Descending frequency within Vehicle;
4. PT in alphabetical order.

Subjects are counted only once for each SOC and PT. In summaries of maximum severity and maximum relationship, subjects with multiple occurrences of events will only be counted once at the maximum severity/relationship per SOC and PT.

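### The two adverse event causality grades overlap and have no tie-break, so the same on-treatment event can be graded Related or Unrelated and the relationship tables say little reliable about causality

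*Protocol*

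**What the plan says.** Protocol 8.2.1.2 has the investigator assess relationship "based on temporal relationship and his/her clinical judgment" and record it in one of two categories. Each category is a list joined by the word or.

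- **Related** is met if the event is known to occur with the product, if there is a reasonable possibility that the product caused it, "or there is a temporal relationship between the IP and event". The next sentence explains the middle criterion: "Reasonable possibility means that there is evidence to suggest a causal relationship between the IP and the AE".
- **Unrelated** is met if there is no reasonable possibility of causation, "no temporal relationship between the IP and event onset, or an alternate etiology has been established".

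SAP 9.5.1.4.1 carries the same two definitions. Neither document says which grade applies when an event satisfies both.

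Three other places bear on this:

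- Protocol 8.2.1.1 makes temporal association part of being an adverse event at all: "temporally associated with the use of study intervention, whether or not considered related to the study intervention".
- Protocol 8.2.1.3 requires the investigator's report of a serious event to assess whether there is a reasonable possibility that the drug caused it. It has the Sponsor report an event as a suspected adverse reaction "only if there is evidence to suggest a causal relationship between the drug and the adverse event".
- The grade feeds reported outputs. Protocol 9.4.3.1 plans separate summaries of treatment-related events. SAP 9.7.1.6.1 plans "the number and percentage of subjects with any AE by worst severity and worst relationship", and tables of all events by system organ class, preferred term and maximum relationship.

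**The concern.** A two-category scale works only if each event belongs in one category. Here one sufficient condition for Related (timing) and one sufficient condition for Unrelated (another established cause) can easily hold together. Take a common cold on Day 10 of daily dosing: it occurs while the subject is on the product, and it has an obvious other cause. One investigator can grade it Related and another Unrelated, and both follow the protocol.

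The timing criterion also undercuts the stricter test beside it. Reasonable possibility is defined by causal evidence, but an event that lacks such evidence still meets Related on timing.

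At stake is what the relationship tables mean. This is a first-in-human, multi-center trial, so a drug-related event rate is likely to be read closely. If the grade depends on which criterion an investigator reaches for, that rate partly reflects how the definitions were read.

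**Working it through.** The documents state no figure on this point, so the check is of the wording. Let four yes/no conditions describe an event, all from Protocol 8.2.1.2:

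- K: known to occur with the product
- R: reasonable possibility that the product caused it
- T: temporal relationship to the product
- A: alternate cause established

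The definitions then read:

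- Related = K or R or T
- Unrelated = (not R) or (not T) or A

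**All combinations.** There are 2 × 2 × 2 × 2 = 16.

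- Related fails only when K, R and T are all no. A is free, so 2 combinations fail.
- Unrelated fails only when R and T are yes and A is no. K is free, so 2 combinations fail.
- The two failing sets do not overlap, so no combination meets neither grade. Both grades are met in 16 − 2 − 2 = 12.

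**Events with a temporal relationship (T = yes).** There are 8 combinations. All 8 meet Related. Unrelated fails in the 2 with R yes and A no, so 8 − 2 = 6 meet both grades, 2 are Related only and none is Unrelated only.

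| | Combinations | Both grades | Related only | Unrelated only |
|---|---|---|---|---|
| All | 16 | 12 | 2 | 2 |
| T = yes | 8 | 6 | 2 | 0 |

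Some combinations are clinically unlikely, for example a reasonable possibility with no temporal relationship. The counts show how the wording behaves and are not event rates.

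**Two routes into the overlap when T = yes.** The first is an alternate cause (A = yes), as with the Day 10 cold. The second needs no alternate cause: if the investigator sees no reasonable possibility (R = no), Unrelated is met on that ground while Related is still met on timing.

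**After the change proposed below.** Related = R and Unrelated = not R. Of the 16 combinations 8 are Related, 8 are Unrelated and none is both; with T = yes the split is 4, 4 and 0.

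**What survives without the label.** The documents give no event rates, so this is an illustration on assumed ones. Let background incidence b be 10% to 40% in every arm and independent drug-attributable incidence d be 20% to 40%. Suppose every on-treatment event is graded Related. The vehicle rate is then b, the active rate is 1 − (1 − b)(1 − d), and the difference is d(1 − b).

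- Smallest: 0.20 × 0.60 = 0.12, or 12 points.
- Largest: 0.40 × 0.90 = 0.36, or 36 points.

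The contrast with vehicle remains, though 20 subjects per arm would detect it with power of only about 11% to 74% over this range.

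**The case against.** The strongest reply is that investigators are not asked to apply the lists mechanically. Clinical judgment is named alongside timing, investigators are masked (Protocol 5.3), and SAP 9.6.1 plans training. The adverse event definition itself separates timing from relatedness. A lean towards Related may also be deliberate: the protocol treats the product as always suspect, and the SAP counts a missing relationship on a treatment-emergent event as Related. Such a lean is defensible in a first-in-human study.

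Much of this limits the consequence but does not remove the defect. Judgment has to be recorded in the two categories, and for many on-treatment events those categories accept either answer. A deliberate lean would need a rule that Related prevails when both fit, and there is none. Whether training or the Manual of Procedures addresses causality grading cannot be seen from these documents.

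Two stronger readings are tempting and not supported:

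- *Nearly every on-treatment event will be Related by definition.* Timing does make each such event eligible for Related, but most of the logical cases are equally eligible for Unrelated, so the text does not force the grade. Events are also recorded from informed consent (Protocol 8.2.1), and those before the first dose have no temporal relationship to the product.
- *The trial's safety tables cannot separate drug effects.* SAP 9.7.1.6.1 presents events by treatment group, including a randomized vehicle arm, and plans all events by system organ class and preferred term without using the label. With masked graders, the documents give no reason to expect grading differences to favour one arm.

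Nor does the overlap reach expedited reporting. Every serious event goes to the Sponsor whether or not it is considered related, with its own reasonable-possibility assessment, and the Sponsor's onward reporting rests on causal evidence.

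**Conclusion.** The point holds as a defect in the classification rule. The grades are not mutually exclusive, no precedence is stated, and 6 of the 8 logical cases with a temporal relationship fit both. The firm consequence is that different investigators can grade the same event differently, so the related-event summary and the worst- and maximum-relationship tables give little reliable information on causality.

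This rests on reading the criteria as written, each sufficient on its own, and on there being no overriding guidance outside the two documents. It does not yield an expected share of events graded Related, nor a size or direction for any error in that share. The all-event tables by arm, expedited reporting and the efficacy analyses stand as planned. It should be corrected because the tables are promised outputs and the correction is cheap.

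**What to change.** In Protocol 8.2.1.2 and SAP 9.5.1.4.1, put both grades on one criterion:

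- **Related:** there is a reasonable possibility that the product caused the event, keeping the existing explanation of that term ("Reasonable possibility means that there is evidence to suggest a causal relationship between the IP and the AE").
- **Unrelated:** there is no such reasonable possibility.

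List timing, known effects of the product and alternate cause as factors the investigator weighs, none of them decisive alone. This brings the grade into line with the assessment that Protocol 8.2.1.3 already requires for serious events.

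The cost is wording in two documents and a line in site training, with no new data, visits or subjects. The one downside is that the reported share of related events may fall, because timing alone would no longer suffice.

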8.2.1.3 Adverse Event Reporting Requirements

According to federal regulations, an Investigator must immediately (within 24 hours) report to the Sponsor or a designee any SAE, whether or not considered drug related, including those listed in the protocol or IB and must include an assessment of whether there is a reasonable possibility that the drug caused the event.

According to federal regulations, the Sponsor must notify the FDA and all participating Investigators as soon as possible, but in no case later than 15 calendar days after the Sponsor determines that a potential serious risk arising from a clinical study qualifies for reporting. Sponsor must report any suspected adverse reaction that is both serious and unexpected. The Sponsor must report an AE as a suspected adverse reaction only if there is evidence to suggest a causal relationship between the drug and the adverse event (See 21 CFR 312.32(c)(1)).

Furthermore, the Sponsor must also notify FDA of any unexpected fatal or life-threatening suspected adverse reaction as soon as possible but in no case later than 7 calendar days after the Sponsor's initial receipt of the information (See 21 CFR 312.32(c)(2)).

8.2.1.4 Pregnancy

All pregnancies are to be reported from the time informed consent is signed until 14 days after the last study visit.

Any report of pregnancy for any female study subject must be reported within 24 hours to the Sponsor or its delegate using the Pregnancy Report Form. The pregnant female study subject must be withdrawn from the study.

Every effort should be made to gather information regarding the pregnancy outcome and condition of the infant. It is the responsibility of the Investigator to obtain this information within 30 calendar days after the initial notification and approximately 30 calendar days after delivery.

Pregnancy complications such as spontaneous abortion/miscarriage or congenital abnormality are considered SAEs and must be reported to the Sponsor or its delegate using the Serious Adverse Event Form. **Note:** An elective abortion is not considered an SAE.

In addition to the above, if the Investigator determines that the pregnancy meets serious criteria, it must be reported as an SAE to the Sponsor or its delegate.

9 Statistical Considerations

Continuous measures will be summarized descriptively by the mean, standard deviation, median, minimum, and maximum values. Categorical measures will be summarized by the frequency and percentage of subjects.

A separate Statistical Analysis Plan (SAP) will be prepared prior to unmasking of study data.

Baseline for computing change from baseline for IOP at each time point will be time-matched.

9.1 Statistical Hypothesis

The null hypothesis is that VVN539 has an equivalent effect compared to vehicle for mean IOP at each diurnal time point (8AM, 10AM, and 4PM) at Visit 4 (Day 7), Visit 5 (Day 14), and Visit 6 (Day 21). The alternative hypothesis is that VVN539 is superior to vehicle for mean IOP at these time points.

9.2 Sample Size Determination

With a sample size in each group of 20, the study will have 80% power to detect a difference of 3.0 mm Hg between an VVN539 dose compared to vehicle at each diurnal time point assuming a common standard deviation of 3.3 mm Hg, $\alpha = 0.05$ (two-tailed).

There is no correction for multiplicity for multiple time points or comparisons for high or low VVN539 doses.

9.3 Analysis Populations

The Full Analysis Set (FAS) consists of all subjects who were randomized. Subjects will be analyzed in the group to which they were randomized. This set will be used for the analysis of all efficacy endpoints as the primary analysis.

The Per Protocol (PP) Analysis Set will include all subjects who completed study-required treatment and who followed the protocol without significant deviations. The determination of significant protocol violations will be made prior to locking the final database and unmasking. Subjects will be analyzed in the group to which they were randomized.

The Safety Analysis Set will include all subjects who took at least one dose of investigational product as indicated on the dosing record. Subjects will be analyzed in the group according to the treatment received. All safety variables will be analyzed using the Safety Analysis Set and only observed data will be included (i.e., missing data will remain missing for the safety analysis).

9.4 Statistical Analyses

The statistical analysis of the study will be performed on the data through Day 21 and will be performed after all subjects have either completed the Day 21 visit or discontinued early from the study and after the study database has been cleaned, verified, and locked. It is planned that the data from all clinical sites that participate in this study will be combined so that the target sample size will be available for analysis.

9.4.1 Baseline Descriptive Analyses

Demographic characteristics including age (years), sex, race, ethnicity, and baseline disease characteristics will be summarized by cohort and overall. Medical history (coded using the most recent version of MedDRA), and prior and concomitant medications (coded using World Health Organization Dictionary) will be summarized by cohort and overall.

The numbers of subjects who were enrolled and completed each visit of the study will be provided, as well as the reasons for all enrollment discontinuations, grouped by major reason (e.g., lost to follow-up, adverse event, poor compliance, rescue due to lack of efficacy). A list of discontinued subjects, protocol deviations, and subjects excluded from the analysis sets will be provided as well.

Exposure and compliance to study treatment will be summarized by treatment and overall.

9.4.2 Efficacy Analyses

Efficacy analyses will be based on the study eye using the FAS.

9.4.2.1 Primary Efficacy Analyses

Primary Estimands: The primary estimands are the treatment differences between VVN539 and vehicle at 8:00 AM, 10:00 AM, and 4:00 PM at each of Days 7, 14, and 21 in the study eye using the FAS. The primary estimands treat subjects as if they do not receive rescue/prohibited therapy.

Target Population: Subjects with open-angle glaucoma or ocular hypertension that meet the study entry criteria.

Endpoint: Observed IOP measurements at each time point in the study eye.

Treatment Condition(s): Treatment condition is based on the randomized treatment group.

Population-level Summaries: The difference in the mean IOP at the nine time points of interest and their corresponding p-values and 95% confidence intervals.

Intercurrent Events and Strategies to Address Intercurrent Events

- Discontinuation of study therapy with continued participation in the study without receipt of prohibited/rescue therapy
 - Treatment Policy – no imputation; use observed data
- Receipt of prohibited/rescue therapy in the study eye
 - Hypothetical Approach – data for visits after the receipt of rescue therapy will be set to missing and will be analyzed assuming missing at random (MAR) using a longitudinal model (mixed model repeated measures, MMRM)
- Missing data without withdrawal or with withdrawal regardless of reason
 - Hypothetical Approach: visits that are missing data will be analyzed assuming MAR using MMRM

Time-matched longitudinal models adjusting for baseline and including a random effect for center will be used to test time-specific comparisons.

Data from Days 7, 14, and 21 will be analyzed using MMRM with an unstructured covariance assumed for each treatment with treatment, visit, and visit by treatment interaction as a fixed effects, baseline measurement as a covariate, and a random effect for site.

Sample code for the model run separately for 8AM, 10 AM, and 4 PM:

```
PROC MIXED DATA=indata;
  CLASS site visit treatment;
  MODEL IOP = baseline visit treatment visit*treatment / solution DDFM=KR;
  REPEATED visit / SUBJECT=subject TYPE=UN group = treatment;
  RANDOM site;
  LSMEANS treatment*visit / slice=visit CL;
RUN;
```

Sensitivity analyses include a time-matched last observation carried forward (LOCF) of the last available IOP measurement as well as analysis of covariance (ANCOVA) analyses at each visit. Additional sensitivity analyses will be performed on the PP Analysis Set as necessary.

